## Section B: Molecular Analyses

To further characterize the tumor samples we will perform FISH on FFPE samples to determine *EGFR* amplification, *PDGFRA* amplification, and *CDKN2A* loss. To examine methylation of the *PTEN* promoter, we will use methylation-specific primers previously used to demonstrate methylation of the *PTEN* promoter in non-small-cell-lung cancer as well as adult and pediatric gliomas (McBride, Perez et al. 2010; Mueller, Phillips et al. 2012). These primers amplify a 181 base pair region of the *PTEN* promoter that starts 2477 nucleotides from the translation start site. The methylation-specific PCR (MSP) assay is sensitive to approximately 5% methylated product.

### Summary of Immunohistochemical and Molecular Assays:

Molecular feature	Assay (reagents)
PTEN expression IHC	Cell Signaling #9559 (Rabbit)
Phosphorylated S6 235/236	IHC: Cell Signaling #2211 (Rabbit)
Phosphorylated S6 240/244	IHC: Cell Signaling #2215 (Rabbit)
Phosphorylated PRAS40 (pT246)	IHC: Cell Signaling #2997 (Rabbit)
Phosphorylated 4EBP1	IHC: Cell Signaling #2855 (Rabbit)
Phosphorylated Erk1/2	IHC: Zymed #18-2389 (Rabbit)
IDH1R132H	IHC: Dianova (DIA H09)
MIB-1 (Ki67)	IHC: Ventana #790-4286

P53	IHC: Dako M7001
ATRX	IHC: Sigma-Aldrich #HPA001906
P53 sequencing, when possible	Sanger sequencing
Sequence cases negative for IDH1 and IDH2 mutations, when IHC negative and sufficient tissue	Sanger sequencing
1p19q deletions	FISH
EGFR	FISH
PDGFRA	FISH
CDKN2A	FISH
PTEN promoter methylation	Methylation-specific primers as described

### Section C: Genomic Analyses: Custom capture Approach

In this clinical trial of everolimus, we propose a radically more in-depth analysis of the pre-treatment tumors using custom capture and sequencing of approximately 300 selected cancer genes including all genes known genes in the PI3K/mTOR pathway, rather than all 20,000 genes captured in exome sequencing. Custom capture has a 10- to 100-fold increased sensitivity for detection of cells harboring mutations in the selected genes relative to exome sequencing. Furthermore, with the custom capture approach, 10 independent exome libraries will be multiplexed with barcodes so all 10 can be deeply sequenced using a single sequencing lane. Thus, with just 3 lanes of sequencing, 30 independent pieces of tumor from a single patient can be assayed.

In a funded NIH study that will be complementary to what we propose in this clinical trial, exome sequencing of up to 2 samples per patient per surgery is being used to define the frequency of TMZ induced hypermutation in a large patient cohort, including patients on this clinical trial. Leveraging the personnel and infrastructure supported by the NIH R01 project at these same surgeries, we will collect up to 5 spatially distinct pieces of tumor at each resection, and macrodissect them each into 6 individual pieces (30 tumor pieces total per patient). This standardization of tissue collection for all newly diagnosed LGG patients at UCSF will ensure that the patients that enroll in this clinical trial (enrollment is post-operative) will have the necessary tissue for in-depth analysis of clonal and subclonal drivers, with emphasis on known components of the PI3K pathway. Not all patients on this trial will have their surgeries at UCSF. For the few cases that are non-UCSF surgeries, we will have fewer tumor pieces to sequence, but they will be sequenced to greater depth.

Because *PTEN* methylation and/or PI3K pathway activation were associated with shorter survival, we will test for an association between the presence/absence of clonal or subclonal genetic mutations in the PI3K pathway and clinical features including Median PFS, Objective Response Rate (ORR), and the immunohistochemical measurements of the PI3K pathway. We

---

will test for potential additive or synergistic effects of *PTEN* methylation and genetic mutation in PI3K pathway activation.

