### 9.5.2 Analysis of Primary Endpoints

**33-(38-)month PFS:** Analyses will be performed after all enrolled patients have completed 33 (38) months on study, or whenever the progression status of all patients has been established, whichever comes first. The primary analysis will be based on Kaplan-Meier method. Kaplan-Meier estimates and the associated 95% CIs will be calculated for the 33-(38-)month PFS separately for the three arms. The Cox proportional hazards model will also be used to allow for adjustment of the prognostic factors including age, KPS, and extent of resection.

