### 9.5.4 Analysis of Exploratory Endpoints

**Metabolic and physiologic imaging parameters:** We will determine if metabolic and physiologic imaging parameters correlate with the clinical endpoints of time to progression and survival. We will assess the usefulness of these parameters in predicting PFS and OS using Cox regression. If the number of patients with responses is sufficient we will also assess the ability of the imaging score to predict response using logistic regression. In addition to the imaging parameters, the models will include: age, KPS, extent of resection, time since diagnosis, Arm 1, 2 vs. 3, and initial diagnostic histology scored as oligodendrogloma only vs. those with an astrocytoma component. The inclusion of these additional variables is to adjust for known or potential confounding risk factors.

**Clonal or subclonal genetic mutations:** We will assess the association between the presence/absence of clonal or subclonal genetic mutations in the PI3K pathway and median PFS, Objective Response Rate (ORR), *PTEN* methylation, and the immunohistochemical measurements of the PI3K pathway activation in patients together and by arm. Tests for association will be used as appropriate including chi-square for proportions and contingency tables and t-tests for continuous valued variables.

**Quality of Life Parameters:** Data from the end of 12 cycles of therapy, the end of 24 cycles of therapy, and one year post-therapy will be compared to baseline data (at study enrollment) to see if there are consistent temporal trends between patients over time in total scores as well as in specific functional domains. Paired T-Tests will be employed to make these comparisons. In addition, variability analyses using all available timepoints will be undertaken to evaluate trends within single patients over time, for total scores as well as specific functional domains.

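### The mutation analysis in 9.5.4 adjusts for neither tissue sampled nor extent of resection, so the link between subclonal PI3K-pathway mutations and PFS may be confounded

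*Combined protocol and SAP*

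**What the plan says.** Appendix 2, Section C describes the tissue: "we will collect up to 5 spatially distinct pieces of tumor at each resection". Each sample is divided into six, for 30 sub-pieces per patient, and the sequencing is planned to match: "with just 3 lanes of sequencing, 30 independent pieces of tumor from a single patient can be assayed". Five is a ceiling, and no minimum is given. The one stated reason for fewer pieces is surgery elsewhere: "For the few cases that are non-UCSF surgeries, we will have fewer tumor pieces to sequence, but they will be sequenced to greater depth". Neither the smaller number nor the greater depth is quantified.

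Section 9.5.4 relates the "presence/absence of clonal or subclonal genetic mutations in the PI3K pathway" to median PFS, ORR, *PTEN* methylation and immunohistochemistry, in all patients and by arm. The methods are given in one sentence: "Tests for association will be used as appropriate including chi-square for proportions and contingency tables and t-tests for continuous valued variables". No covariate and no term for sampling effort is named.

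Elsewhere the plan treats extent of resection as prognostic. Section 9.5.2 adds a Cox model for PFS with "adjustment of the prognostic factors including age, KPS, and extent of resection". The imaging paragraph of 9.5.4, immediately before the mutation paragraph, also includes extent of resection, as a known or potential confounder. Section 1.1 lists it among the factors that influence survival.

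**The concern.** A subclone occupies only part of a tumour, and Section 2.2 expects the relevant alterations to sit in rare cells. Whether it is found depends on whether a sampled region contains it. More reads from one region reveal rarer cells in that region and say nothing about the rest of the tumour. Two patients with identical tumours can therefore receive different mutation status because different amounts of tissue were searched.

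Unequal detection that is unrelated to outcome only dilutes associations. It becomes confounding if patients with more samples also have better PFS for another reason. Extent of resection is the obvious candidate: a larger resection could supply more samples and is treated by the plan as prognostic. Mutation-present would then partly stand for better resected and would look favourable.

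That direction matters for interpretation. It could hide an adverse effect, which Appendix 2, Section C has in mind when it cites shorter survival with pathway activation. It could also imitate the hypothesis in Section 2.1 that pathway activation predicts benefit from mTOR inhibition.

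**Working it through.** **Figures in the plan.** 5 samples × 6 = 30 sub-pieces, and 3 lanes × 10 libraries = 30. The stated maximum reproduces. The documents give no distribution of sample counts, so everything below rests on assumed inputs.

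**Step 1: detection.** Let q be the chance that one sample contains the subclone. With k independent samples, detection is 1 − (1 − q)^k.

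| q (assumed) | 1 sample | 2 | 3 | 5 |
|---|---|---|---|---|
| 0.1 | 10% | 19% | 27% | 41% |
| 0.3 | 30% | 51% | 66% | 83% |
| 0.5 | 50% | 75% | 88% | 97% |

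For a clonal mutation q is near 1 and the number of samples hardly matters. If all sub-pieces were independent with q = 0.05, detection would be 79% from 30 and 26% from 6. Six sub-pieces of one sample are neighbours, however, so the effective range is nearer 1 to 5.

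**Step 2: spurious PFS-33 difference.** Assume that the mutation has no effect on PFS, that PFS-33 is 75% in patients with more tissue and 60% in those with less, and that a patient is positive if any piece is positive. Let w be the share of low-tissue patients, v the true prevalence of carriers, and D_H and D_L the detection probabilities. Then:

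- PFS-33 in positives = [(1 − w)·v·D_H·0.75 + w·v·D_L·0.60] / [(1 − w)·v·D_H + w·v·D_L]
- PFS-33 in negatives: the same, with 1 − v·D in place of v·D

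Worked cases:

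- 30 v 6 independent pieces, q = 0.05, w = 0.5, v = 1: positives (0.785×0.75 + 0.265×0.60)/1.050 = 71.2%; negatives (0.215×0.75 + 0.735×0.60)/0.950 = 63.4%; gap 7.8 points.
- 5 v 1 samples, q = 0.5, w = 0.5, v = 1: positives (0.969×0.75 + 0.5×0.60)/1.469 = 69.9%; negatives (0.031×0.75 + 0.5×0.60)/0.531 = 60.9%; gap 9.0 points.
- 5 v 1 samples, q = 0.05, w = 0.1, v = 0.5: 74.6% against 73.4%; gap 1.3 points.

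Gap in percentage points:

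| Contrast | q | w=0.5, v=1 | w=0.5, v=0.5 | w=0.1, v=1 | w=0.1, v=0.5 |
|---|---|---|---|---|---|
| 30 v 6 independent pieces | 0.05 | 7.8 | 5.0 | 3.6 | 1.5 |
| 5 v 1 samples | 0.05 | 5.6 | 5.1 | 1.4 | 1.3 |
| 5 v 1 samples | 0.1 | 6.1 | 5.2 | 1.8 | 1.4 |
| 5 v 1 samples | 0.3 | 8.1 | 4.9 | 4.2 | 1.5 |
| 5 v 1 samples | 0.5 | 9.0 | 3.8 | 8.8 | 1.3 |

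The same formula for q from 0.1 to 0.5 gives 0.6 to 6.8 points for 5 v 2 samples and about 0.25 to 4.9 for 5 v 3.

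**Step 3: hazard ratios by simulation.** Assumptions: half the patients have a larger resection and give 5 samples, the rest give 1, 2 or 3; true prevalence is 50%; q runs from 0.1 to 0.5; the resection hazard ratio for PFS is 0.4 to 0.67; the true mutation hazard ratio is 1.0; censoring falls between 38 and 91 months. Rejection rates come from 800 simulated trials of 105 patients per scenario.

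| Samples | Unadjusted HR, mutation present | Rejection rate of nominal 5% test, N = 105 |
|---|---|---|
| 1 v 5 | 0.73 to 0.90 | about 5 to 15% |
| 2 v 5 | 0.81 to 0.96 | about 4 to 8% |
| 3 v 5 | 0.89 to 0.98 | about 4 to 8% |

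Stratifying by extent of resection brings the hazard ratio back to 0.98 to 1.04 in every scenario.

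**The case against.** The strongest reply is that the decisive link is missing. A reader might infer from the cap of five that small resections give fewer samples, but no section says so. The only documented low-tissue group is defined by where surgery took place, and those cases are called few. Appendix 2, Section C also describes standardised collection for newly diagnosed patients at the centre, and any two resections that both supply five samples are searched equally. The evaluable-disease criterion may narrow the range of resection further. All of this stands: the documents support saying that the association may be confounded, not that it is.

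A reader might also infer that a patient counts as positive if any piece is positive. That is the natural reading of presence or absence, but no calling rule is stated. Likewise, an 8-point bias should not be taken as the expected size. It requires that every patient carries a subclone, that half give only six pieces and that all 30 sub-pieces behave independently. With 10% low-tissue patients the same calculation gives 3.6 points, and with 50% prevalence as well, 1.5.

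Finally, the list of tests in 9.5.4 is open-ended, so an adjusted model is not excluded, and the aim is exploratory. Both points are fair. The open list still leaves a plain inconsistency: the imaging paragraph specifies adjustment for extent of resection and the mutation paragraph does not.

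**Conclusion.** The point holds as a low-priority one. Subclonal status depends on the number of spatially distinct samples, depth offsets this only in part, and the mutation analysis names no adjustment for sampling effort or for a factor that the plan itself treats as prognostic. If sample count tracks extent of resection, the bias makes mutation-present look favourable. Its size is about 1 to 9 points of PFS-33 when low-tissue patients give one sample against five, and smaller with two or three. Those sizes rest wholly on assumed values for detection, prevalence, the share of low-tissue patients and the effect of resection. False-positive inflation at 105 patients is modest.

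The concern is confined to the subclonal part of this exploratory objective. The illustration covers PFS only and makes no estimate for ORR, *PTEN* methylation or immunohistochemistry. Nothing here touches PFS-33, PFS-38 or the secondary endpoints.

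**What to change.** In 9.5.4, replace the unadjusted tests of mutation status with a Cox model for PFS and a logistic model for ORR. Each should include extent of resection, as the imaging models already do, and number of samples sequenced. The Cox model also handles censored PFS, which chi-square and t-tests do not. State the rule for calling a patient positive, and record samples, sub-pieces and depth per patient. Report clonal and subclonal mutations separately.

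Adjustment removes the spurious association but does not recover subclones that were missed, so a true effect may still be diluted. Status at a common sampling effort is therefore worth adding as a sensitivity analysis. It should not be the main analysis, because the common level is set by patients with least tissue and would discard the multi-region sampling designed to find rare subclones.

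The cost is wording, analysis code and one or two extra terms in an exploratory model. Precision falls slightly, most noticeably in the by-arm analyses of 35 patients. Treatment, visits and sample size do not change.

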## **Appendix 3: Data and Safety Monitoring Plan for Phase 2 or 3 Inst. Study**

The UCSF Helen Diller Family Comprehensive Cancer Center (HDFCCC) Data and Safety Monitoring Committee (DSMC) is responsible for monitoring data quality and subject safety for all HDFCCC institutional clinical studies. A summary of DSMC activities for this study include:

- Review of subject data
- Review of suspected adverse reactions considered “serious”
- Monitoring every six months (depending on study accrual)
- Minimum of a yearly regulatory audit

### **Monitoring and Reporting Guidelines**

Investigators will conduct continuous review of data and subject safety and discuss each subject's treatment at monthly Site Committee meetings. These discussions are documented in the Site Committee meeting minutes. The discussion will include the number of subjects, significant toxicities in accordance with the protocol, and observed responses.

All institutional Phase 2 or 3 studies are designated with a moderate risk assessment. The data is monitored twice per year with twenty percent of the subjects monitored (or at least three subjects if the calculated value is less than three).

#### **Adverse Event Review and Monitoring**

All grade(s) 3-5 adverse events, whether or not unexpected, and whether or not considered to be associated with the use of the study drug, will be entered into OnCore®, UCSF's Clinical Trial Management System.

All grade(s) 3-5 adverse events entered into OnCore® will be reviewed on a monthly basis at the Site Committee meetings. The Site Committee will review and discuss the selected toxicity, the toxicity grade, and the attribution of relationship of the adverse event to the administration of the study drug(s).

In addition, all suspected adverse reactions considered “serious” entered into OnCore®, will be reviewed and monitored by the Data and Safety Monitoring Committee on an ongoing basis and discussed at DSMC meetings, which take place every six weeks.

If a death occurs during the treatment phase of the study or within 30 days after the last administration of the study drug(s) and it is determined to be related either to the study drug(s) or to a study procedure, the Investigator or his/her designee must notify the DSMC Chair within **1 business day** of knowledge of this event. The contact may be by phone or e-mail.

#### Appendix 4: Temozolomide Package Insert

[http://www.merck.com/product/usa/pi\\_circulars/t/temodar\\_capsules/temodar\\_pharm.pdf](http://www.merck.com/product/usa/pi_circulars/t/temodar_capsules/temodar_pharm.pdf)
